5.2 Interim Analysis

No formal statistical interim analyses are planned, however, data will be monitored by the Safety Monitoring Committee (SMC) to assess patient safety for Run-in cohort before enrolment into Arm A can start and for dose escalation within Arm A.

5.3 Disposition of Subjects

The number of subjects receiving study treatment in each analysis population and the reasons for any discontinuation from the study will be summarized by treatment arm.

5.4 Baseline and Demographic Characteristics

All baseline and demographic characteristics will be summarized. This will include age, age group, sex, ethnicity, race, height, weight, and Eastern Cooperative Oncology Group (ECOG) performance status at screening. Cancer history (Histologic Diagnosis, Stage at initial diagnosis, Stage at screening and sites), medical history by system organ class and preferred term, Mutation status and prior cancer therapies (chemotherapy, hormonal therapy, immunotherapy, monoclonal therapy, radiotherapy, other therapy, surgery) will also be summarized.

Notes:

- Age (years) will be calculated as (Date Informed Consent - Date of Birth + 1)/365.25.
- Age groups are defined as: <65 years and \geq 65 years of age.
- Medical history will be coded according to Medical Dictionary for Regulatory Activities (MedDRA) version 15.0 or above.
- Prior cancer therapies will be coded using World Health Organization (WHO) Drug Dictionary, Mar 2014 or above.

5.5 Concomitant Medication

Medications taken on or after date of informed consent are collected. Prior medications are those that started and stopped before exposure to study medication; concomitant medications are all medications taken during the study period, including those started before but ongoing at first dose.

Incidence of concomitant medication will be presented therapeutic area and preferred drug name. Where a medication start date is partially or fully missing, and it is unclear as to whether the medication is prior or concomitant, it will be assumed that it is concomitant. Medications will be coded using WHO Drug Dictionary, Mar 2014 or above.

5.6 Exposure and Compliance

BGB324 exposure will be summarized by the number of cycles started on BGB324/Erlotinib and duration of administration by dose cohort. Duration (days) of BGB324/Erlotinib administration will be defined as:

Date of Last Study Drug Administration – Date of First study Drug Administration + 1 day

Total treatment exposure to BGB324/Erlotinib will also be characterized by total cumulative dose (mg) over the whole study and summarized by dose cohort.

Study drug percent compliance for BGB324/Erlotinib will be calculated as:

$((\text{Expected number of doses} - \text{Missed number of doses}) / \text{Expected number of doses}) * 100$,

where Expected Number of Doses is defined as duration of study drug administration in days at each cycle, i.e 21 days;

Missed number of doses will be calculated as Last date of missed - First Date Missed;

Overall percent compliance will be summarized by frequency count and percentage of subjects with compliance <80%, 80 to 120% and >120%. Overall percent compliance will also be summarized as a continuous variable using descriptive statistics.

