11.3.1.2 BGB324 daily dose toxicities

Recommended BGB324 dose modifications are provided in Table 7 and Table 8.

If, after a 14-day delay, treatment-related toxicity has not resolved, the patient may be discussed with the Medical Monitor prior to being withdrawn from the study.

For those patients who experience a BGB324 dose delay of ≥ 7 days, the BGB324 loading dose assigned should be repeated. If the patient was unable to tolerate the loading dose in Cycle 1 the repeat loading dose can be omitted. The requirement to reintroduce the loading dose should be discussed with the Medical Monitor.

Drug holidays for reasons other than BGB324 or erlotinib toxicity may be permitted on a case--by-case basis and should be discussed with the Medical Monitor.

Table 7 Daily Dose Modification of BGB324 for Toxicity

Grade (CTCAE)	Recommended Dose Modification
Grade 1 and Grade 2 (tolerable)	
Any occurrence	Maintain dose if toxicity is tolerated by the patient
Grade 2 (intolerable)	
1 st or 2 nd occurrence of same event	Interrupt treatment until toxicity returns to baseline, Grade 1 or tolerable Grade 2. Resume dosing at same dose
3 rd occurrence of same event	Interrupt treatment until toxicity returns to baseline, Grade 1 or tolerable Grade 2. Dose reduce by 100 mg

Grade (CTCAE)	Recommended Dose Modification
4th occurrence of same event	Discontinue permanently
Grade 3	
1 st occurrence	Interrupt treatment until toxicity returns to baseline, Grade 1 or tolerable Grade 2. Dose reduce by 100 mg or, Discontinue permanently if dose has already been reduced
2 nd occurrence of same event at Grade 3	Discontinue permanently
Grade 4	
1 st occurrence	Discontinue permanently
Notes:	

 • Treatment interruption for BGB324-related toxicity should be limited to 14 days, • Dose reduction below 100 mg daily is not possible (a single capsule contains 100 mg BGB324), • Patients being considered for dose reduction or permanent discontinuation of BGB324, may be discussed with the Medical Monitor, 	

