11.3.1.4 BGB324 dose modification for steroids doses over 40mg daily (prednisolone equivalent)

If a patient requires prednisolone (or equivalent) at daily doses above 40mg then BGB324 should be interrupted until the steroid dose is equivalent to or less than 40mg daily, at which time weekly monitoring will be undertaken until the steroid dose is equivalent or less than 10mg (Section 10.1.8)

For those patients who experience a BGB324 dose delay of ≥7 days, the BGB324 loading dose assigned should be repeated. If the patient was unable to tolerate the loading dose in Cycle 1 the repeat loading dose can be omitted. The requirement to reintroduce the loading dose should be discussed with the Medical Monitor.

Steroid restrictions do not apply to topical/ inhaled/ eye or nasal drops. If required, additional advice on the concomitant use of steroids with BGB324 should be obtained from the BerGenBio Medical Monitor.

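### SAP 5.6 counts withheld days as days of administration and must score a directed hold as either missed or taken, so duration and compliance are misdescribed for patients who were interrupted and resumed

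*SAP*

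**What the plan says.** SAP 5.6 plans three descriptive measures of exposure for BGB324 and erlotinib: cycles started, duration, and cumulative dose.

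- Duration is "Date of Last Study Drug Administration – Date of First study Drug Administration + 1 day", with no term for interruptions.
- On cumulative dose: "Total treatment exposure to BGB324/Erlotinib will also be characterized by total cumulative dose (mg) over the whole study and summarized by dose cohort". No planned-dose denominator is given.
- Compliance is expected minus missed doses, divided by expected doses, times 100, "where Expected Number of Doses is defined as duration of study drug administration in days at each cycle, i.e 21 days".
- On the other input: "Missed number of doses will be calculated as Last date of missed - First Date Missed". Nothing says whether a dose withheld on instruction is a missed dose.
- Overall compliance is grouped as below 80%, 80 to 120% and above 120%.

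The protocol directs interruptions. For intolerable Grade 2 and for Grade 3 toxicity, Table 7 in section 11.3.1.2 instructs: "Interrupt treatment until toxicity returns to baseline, Grade 1 or tolerable Grade 2". Its notes add: "Treatment interruption for BGB324-related toxicity should be limited to 14 days". Table 8 in section 11.3.1.3 directs holds of up to 14 days for QTcF prolongation. Section 11.3.1.4 covers steroids: "BGB324 should be interrupted until the steroid dose is equivalent to or less than 40mg daily". It states no maximum length. Section 11.3.1.2 also allows drug holidays for other reasons, case by case.

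**The concern.** A hold followed by resumption lies between the first and last dose dates, so duration counts each withheld day as a day of administration. The patients affected are those who were interrupted, often for toxicity, and then restarted.

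Compliance has a related gap. With 21 expected doses in every cycle, a withheld day can be handled in only two ways. If it is entered as missed, a patient who followed every instruction loses compliance. If it is not entered as missed, it stays in the numerator as though a dose had been taken. The same clinical course can therefore produce different results depending on how the missed-dose field is completed.

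Safety and tolerability is the primary objective of the Run-in Cohort and of Arms B and C, and a secondary objective of Arm A. At stake is whether the exposure and compliance tables (14.1.7.x and 14.1.8) let a reader tell poor adherence from poor tolerability. As defined, Table 14.1.8 does not.

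**Working it through.** The SAP gives no numerical exposure or compliance result, so there is no figure to reproduce. The check applies the SAP 5.6 formulas to example patients.

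**Inputs**
- Cycle length 21 days (protocol 8.8, SAP 5.6).
- One hold of 14 days, the limit in the Table 7 notes; 7 days as a shorter case. Both lengths are assumptions, since the documents give no hold frequencies.
- The patient takes every dose that is not withheld, resumes after the hold, and doses to the last day of the final cycle.
- The cycle clock runs through the hold. Protocol 8.8 describes continuous cycles, and neither document says that a hold pauses them.

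**Step 1: duration.** The SAP value is 21 × cycles. Dosing days are 21 × cycles − hold.

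| Cycles | SAP duration | Dosing days, 14-day hold | Overstatement |
|---|---|---|---|
| 2 | 42 | 28 | 14/28 = 50.0% |
| 3 | 63 | 49 | 14/49 = 28.6% |
| 4 | 84 | 70 | 14/70 = 20.0% |
| 8 | 168 | 154 | 14/154 = 9.1% |
| 17 | 357 | 343 | 14/343 = 4.1% |

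A 7-day hold gives 7/35 = 20.0% over 2 cycles and 7/77 = 9.1% over 4.

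**Step 2: compliance, hold scored as missed.** Last minus first missed date gives 14 − 1 = 13 missed doses.
- 2 cycles: (42 − 13)/42 = 69.0%
- 3 cycles: (63 − 13)/63 = 79.4%
- 4 cycles: (84 − 13)/84 = 84.5%

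Counting the days inclusively (14 missed) gives 66.7%, 77.8% and 83.3%, so the classes do not change. The patient is below 80% through 3 cycles and above it from 4. A 7-day hold gives (21 − 6)/21 = 71.4% over 1 cycle and (42 − 6)/42 = 85.7% over 2.

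**Step 3: compliance, hold not scored as missed.** The result is 100% at any length of treatment. Over 2 cycles, 14 of the 42 doses treated as taken (33%) were withheld; over 3 cycles, 14 of 63 (22%).

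**Step 4: a patient who also skips doses.** Suppose that, over 2 cycles with a 14-day hold, the patient also misses 4 consecutive prescribed doses. These count as 3 under last minus first.
- Hold as missed: (42 − 13 − 3)/42 = 61.9%
- Hold as taken: (42 − 3)/42 = 92.9%
- Adherence to prescribed doses: (28 − 4)/28 = 85.7%

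The two possible SAP results fall on either side of the true value.

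**Step 5: if the clock paused instead.** Two cycles would then hold 42 dosing days in 56 calendar days, and duration would still be overstated, by 14/42 = 33%. Scoring the hold as not missed would correctly give 100%; scoring it as missed would still give 69.0%. The compliance argument therefore depends partly on this assumption, and the duration argument does not.

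**Step 6: cumulative mg.** A withheld day adds 0 mg, so this measure does not count hold days as exposure.

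**The case against.** Four points on the other side carry weight.

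- **The safety results do not use these measures.** SAP 5.1 takes percentages over subjects in the cohort, and SAP 5.8.1 tabulates adverse events by number and percentage of patients. No exposure-adjusted rate is planned. A reader might infer that adverse event rates are diluted by inflated exposure; the documents do not support that.
- **Only one measure of exposure is inflated.** Cumulative mg excludes withheld days, and the calendar formula is openly stated. A reader might infer that exposure as a whole is overstated; only duration is.
- **Holds may not be scored as missed.** A reader might infer that the plan labels toxicity management as patient non-compliance. That follows only if holds are entered as missed, and the eCRF completion guidelines are not among the documents. On the other reading compliance is inflated.
- **Holds are visible elsewhere.** Tables 14.1.7.4 and 14.1.7.5 cover dose modification, under which the protocol places interruptions, and Listing 16.2.5.4 shows BGB324 administration by cycle.

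All four limit the consequence, but they leave the derivation rules as they are. The dose-modification tables are titles with no defined content, and nothing links them to duration or compliance. Cumulative mg without a planned dose mixes holds, reductions and treatment length. The plan itself draws the missing distinction elsewhere: for Arm A evaluability, protocol 8.3.2 and SAP 3.1 set aside doses not given because of treatment-related toxicity.

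**Conclusion.** The point holds for duration and compliance, and only there. Duration includes every withheld day that is followed by resumption. A hold that ends in permanent discontinuation falls after the last dose and adds nothing. Compliance with a directed hold is undefined, and with the clock running neither available score measures adherence to prescribed doses.

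The size depends on treatment length. It is large in short courses and fades to about 4% of duration at 17 cycles for a single 14-day hold. Repeated holds, which Table 7 allows, or a long steroid-related hold would add to it. The documents give no frequency of holds, so an arm-level effect cannot be calculated. For scale, at the planned maximum sizes one reclassified patient moves the share below 80% by 1/25 = 4.0 percentage points in Arm B and 1/14 = 7.1 in Arm C.

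The effect is confined to Tables 14.1.7.x and 14.1.8. Adverse event percentages, DLT counts and efficacy results are unchanged. The change is still worth making before analysis, because the present rule gives a wrong description rather than merely an incomplete one. No dose or interruption rule is in question.

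**What to change.** Amend SAP 5.6 as follows.

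1. Define expected doses as the days on which a dose was prescribed, excluding days withheld under protocol 11.3 or an agreed drug holiday. Count missed days inclusively, since last minus first gives 0 for a single missed day.
2. Keep calendar duration and add dosing days, defined as duration minus withheld and missed days.
3. For each drug, report relative dose intensity as cumulative mg divided by the originally assigned mg over the full calendar duration, withheld days included. The denominator matters: at a constant daily dose with no loading dose, one 14-day hold in 42 days gives 28/42 = 66.7%, but dividing by dosing days alone gives 28/28 = 100% and hides the hold. State how a repeated loading dose enters the ratio.
4. Show withheld days and their reasons in Tables 14.1.7.4 and 14.1.7.5.

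The cost is SAP wording and a little programming. Dosing diaries are kept, and administration listings and dose-modification tables are already planned. Confirm that the eCRF records the reason for a withheld dose. Reported exposure will look slightly less favourable.

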4.2.1 Treatment Schedule and Administration of BGB324

BGB324 will be self-administered orally on an empty stomach according to a daily schedule during continuous 21-day treatment cycles.

The BGB324 dose will be based on the cohort and study arm to which the patient is enrolled. BGB324 should be administered with water in the morning at least 2 hours before breakfast and best efforts should be made to administer BGB324 at the same time each day, other than study visit days when BGB324 should be administered during the visit.

Patients will record their dosing at home in a dosing diary that will be reviewed at each study visit by the site staff. Patients will be instructed as to the importance of following the dosing instructions they have been provided with and for maintaining an accurate and up-to-date dosing record. Patients will also be instructed to bring their dosing diary and all BGB324 bottles, including unused and empty bottles, with them to each study visit. The site staff will record the amount of used and unused BGB324 capsules at study visits.

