4.2.2 Treatment Schedule and Administration of Erlotinib

Erlotinib will be self-administered orally with BGB324 on an empty stomach according to a daily schedule during continuous 21-day treatment cycles. Best efforts should be made to administer erlotinib in the morning at the same time each day, other than on the morning of study visit days when erlotinib should be administered during the visit. Erlotinib should be administered with water. Patients will be instructed to take their erlotinib dose first followed by BGB324 within the next hour.

Patients will record their dosing at home in a dosing diary that will be reviewed at each study visit by the site staff. Patients will be instructed as to the importance of following the dosing instructions they have been provided with and for maintaining an accurate and up-to-date dosing record. Patients will also be instructed to bring their dosing diary and all boxes of erlotinib, including unused and empty boxes, with them to each study visit. The site staff will record the amount of used and unused erlotinib at study visits.

The details for management of dose modification are specified in the protocol section 11.3.

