6.1 Tables

6.1.1 Section 14.1: Demographic and baseline

Table 14.1.1.1	Subject Disposition (Enrolled Population)
Table 14.1.1.2	Important Protocol Violations (Enrolled Population)
Table 14.1.2	Demographics (Safety Population)
Table 14.1.3	Cancer History (Safety Population)
Table 14.1.4	Medical History (Safety Population)
Table 14.1.5	Prior Cancer Therapies (Safety Population)
Table 14.1.6.1	Prior Medications (excluding anti-cancer therapies)
Table 14.1.6.2	Concomitant Medications (Safety Population)
Table 14.1.7.1	Summary of Exposure to BGB324 (Safety Population)
Table 14.1.7.2	Summary of Exposure to Erlotinib (Safety Population)
Table 14.1.7.3	Summary of Exposure : Number of participants by cycle (Safety Population)
Table 14.1.7.4	Summary of dose modification during the study (Safety Population)
Table 14.1.7.5	Summary of Erlotinib dose modification during the study (Safety Population)
Table 14.1.8	Compliance (Safety Population)

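### The SAP's missed-dose formula leaves out the +1, so each unbroken gap is counted one dose short and compliance in Table 14.1.8 is overstated

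*SAP*

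**What the plan says.** SAP 5.6 defines percent compliance, for BGB324 and for erlotinib, as expected doses minus missed doses, divided by expected doses, times 100. Its two inputs are:

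- Expected doses: "where Expected Number of Doses is defined as duration of study drug administration in days at each cycle, i.e 21 days".
- Missed doses: "Missed number of doses will be calculated as Last date of missed - First Date Missed".

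Overall compliance is then reported as a continuous variable and in three classes: below 80%, 80 to 120% and above 120%. The planned output is Table 14.1.8, on the Safety Population.

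The duration formula earlier in the same section is "Date of Last Study Drug Administration – Date of First study Drug Administration + 1 day". The age formula in SAP 5.4 also adds a day ("Age (years) will be calculated as (Date Informed Consent - Date of Birth + 1)/365.25"), as do both time-to-progression formulas in SAP 5.7.3.2.

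Dosing is daily for both drugs. SAP 4.2.1 states "BGB324 will be self-administered orally on an empty stomach according to a daily schedule during continuous 21-day treatment cycles", and SAP 4.2.2 gives erlotinib the same daily schedule.

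**The concern.** With one dose a day, the number of doses missed in an unbroken gap is the number of calendar days in it, counting both ends. Subtracting the first date from the last gives one fewer. The plainest case is a single missed day: the two dates are equal, the difference is zero, and the patient is scored as fully compliant.

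The compliance ratio then mixes two counting rules. The 21 expected doses per cycle count both end days, and the missed doses do not.

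The section is also silent on patients with more than one gap. It names one last date and one first date and does not say that the formula applies to each gap and is then added up.

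At stake is the accuracy of one descriptive table, including its below-80% class, in a study whose Arm B and Arm C primary objectives are safety and tolerability.

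**Working it through.** **Inputs.** One dose per day of each drug (SAP 4.2.1, 4.2.2), so one missed date is one missed dose. Expected doses N = 21 per cycle (SAP 5.6). Compliance = 100 × (N − missed) / N (SAP 5.6). The documents state no compliance result, so there is no plan figure to reproduce.

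**Step 1: which convention the denominator uses.** Day 1 to Day 21 is 21 − 1 + 1 = 21 days when both ends are counted, and 21 − 1 = 20 by plain subtraction. The SAP uses 21, so its denominator is inclusive.

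**Step 2: error per gap.** A gap of m days that starts on day a ends on day a + m − 1. The SAP formula gives (a + m − 1) − a = m − 1, one dose short whatever the length. With g gaps the count is short by g, and compliance is overstated by 100 × g / N points. For one gap:

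- 1 cycle: 100/21 = 4.8 points
- 2 cycles: 100/42 = 2.4 points
- 3 cycles: 100/63 = 1.6 points
- 6 cycles: 100/126 = 0.8 points

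**Step 3: when the below-80% class is missed.** With m doses truly missed, a patient belongs below 80% when m > 0.2N. The SAP places the patient at 80% or above when m − g ≤ 0.2N. The class is wrong when both hold. For one gap:

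| Expected N | 0.2N | Truly missed | Counted | True compliance | SAP compliance |
|---|---|---|---|---|---|
| 21 | 4.2 | 5 | 4 | 16/21 = 76.2% | 17/21 = 81.0% |
| 42 | 8.4 | 9 | 8 | 33/42 = 78.6% | 34/42 = 81.0% |
| 63 | 12.6 | 13 | 12 | 50/63 = 79.4% | 51/63 = 81.0% |
| 126 | 25.2 | 26 | 25 | 100/126 = 79.4% | 101/126 = 80.2% |

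With two gaps in one cycle the class is missed at m = 5 or 6. For example, days 5–7 and 14–16 are 6 missed doses, counted as 2 + 2 = 4: true 15/21 = 71.4%, SAP 17/21 = 81.0%. Five separate one-day misses in one cycle are counted as 0: true 16/21 = 76.2%, SAP 100%.

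**Step 4: the other reading, one span from first to last missed date.** In one 21-day cycle:

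- Two missed days: there are 21 − d pairs at distance d. Distance 1 (20 pairs) is under-counted, distance 2 (19 pairs) is exact, and the other 210 − 39 = 171 are over-counted.
- Three missed days: there are (21 − s)(s − 1) patterns with span s. Span 2 (19) is under-counted, span 3 (36) is exact, and the other 1330 − 55 = 1275 are over-counted.

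An extreme case is days 3 and 18: 15 counted, 6/21 = 28.6%, against a true 19/21 = 90.5%.

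For a patient with one unbroken gap the two readings coincide, and the count is one dose short under both.

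**The case against.** The strongest objection is about direction. SAP 5.6 mentions neither intervals nor summation, so overstatement is certain only for a patient with a single unbroken gap. For a patient with several gaps, a programmer who took the text as one span would usually understate compliance. The documents also do not show how missed doses are recorded in the eCRF, and the per-gap figures assume one interval per gap. This stands as a condition on the direction. It does not rescue the formula, which gives wrong values for most patterns under the one-span reading too and scores a single missed day as zero under both.

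Second, the comparison with other date counts can be pressed too far. SAP 3.2.3 describes time to progression as a number of days without any added day, and age is elapsed time rather than a count of doses. That is fair. The comparison that matters is the duration formula in SAP 5.6 itself.

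Third, the last missed date might be meant as the day dosing resumed, which would make the subtraction correct. Nothing in either document says so, and the words name a missed date.

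Fourth, a programmer might simply add the day. That would be a departure from the SAP, and SAP 5.13 requires departures to be described and justified in the study report.

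Finally, the effect is small. That is agreed: a class changes only when missed doses exceed 20% of expected by no more than the number of gaps. Duration and cumulative dose are defined separately, and administration is also listed by subject (for example Listing 16.2.5.4).

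**Conclusion.** The concern holds, as a minor error. Followed literally, the rule under-counts each unbroken gap by one dose, and nothing elsewhere in the protocol or SAP corrects it. Applied per gap, it overstates compliance by 4.8 points per gap for a patient treated for one cycle, falling to 0.8 points over six cycles, and it can move a patient out of the below-80% class.

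These sizes rest on three assumptions: each unbroken gap is recorded as one interval, all cycles are complete with 21 expected doses, and every recorded missed day counts as a missed dose. For patients with several gaps the direction also depends on the per-gap reading, which the SAP should state.

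The reach is limited to Table 14.1.8. No hypothesis test, analysis population or stopping rule is stated to use this compliance figure.

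**What to change.** In SAP 5.6, define missed doses as the sum, over all missed-dose intervals in all cycles, of last date missed minus first date missed plus 1. This supplies the missing day and settles how several gaps are handled.

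The cost is one line in the SAP and one in the program. If the per-gap reading was intended, the missed-dose count rises by one per gap and reported compliance falls accordingly.

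The change does not settle two related points on which SAP 5.6 is silent: whether protocol-directed interruptions count as missed doses, and how many doses are expected in an incomplete last cycle.

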11.1 Treatment Schedule and Administration of BGB324

BGB324 will be self-administered orally on an empty stomach according to a daily schedule during continuous 21-day treatment cycles.

The BGB324 dose will be based on the cohort and study arm to which the patient is enrolled. BGB324 should be administered with water in the morning at least 2 hours before breakfast and best efforts should be made to administer BGB324 at the same time each day, other than study visit days when BGB324 should be administered during the visit.

Patients will record their dosing at home in a dosing diary that will be reviewed at each study visit by the site staff. Patients will be instructed as to the importance of following the dosing instructions they have been provided with and for maintaining an accurate and up-to-date dosing record. Patients will also be instructed to bring their dosing diary and all BGB324 bottles, including unused and empty bottles, with them to each study visit. The site staff will record the amount of used and unused BGB324 capsules at study visits.

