13.4.8 Overdoses

Study drug overdose is the accidental or intentional use of the drug in an amount higher than the dose being studied. An overdose or incorrect administration of study drug is not an AE unless it results in untoward medical effects. An overdose is defined by a boundary of 15% above the prescribed dose of any medicinal product.

Any study drug overdose or incorrect administration of study drug should be noted on the Study Drug Administration eCRF. All AEs associated with an overdose or incorrect administration of study drug should be recorded on the AE eCRF. If the associated AE fulfills serious criteria, the event should be reported to the Sponsor immediately (i.e., no more than 24 hours after learning of the event).

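### SAP 5.6 compliance cannot exceed 100%, so the above-120% class is always empty, and a final cycle cut short is misstated by the fixed 21-day denominator

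*SAP*

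**What the plan says.** SAP section 5.6 introduces one formula for both drugs ("Study drug percent compliance for BGB324/Erlotinib will be calculated as"): 100 × (expected doses − missed doses) / expected doses. Its two terms are defined as follows.

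- Expected: "Expected Number of Doses is defined as duration of study drug administration in days at each cycle, i.e 21 days".
- Missed: "Missed number of doses will be calculated as Last date of missed - First Date Missed".

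The result is summarised as a continuous variable and in classes: "Overall percent compliance will be summarized by frequency count and percentage of subjects with compliance <80%, 80 to 120% and >120". The output is Table 14.1.8 (Safety Population).

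For exposure, the same section defines duration differently, ending at the actual last dose: "Date of Last Study Drug Administration – Date of First study Drug Administration + 1 day". It also summarises total cumulative dose in mg.

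Protocol section 13.4.8 sets an overdose limit ("An overdose is defined by a boundary of 15% above the prescribed dose of any medicinal product") and has overdoses noted on the Study Drug Administration eCRF. Protocol section 11.1 provides for dosing diaries and capsule counts ("The site staff will record the amount of used and unused BGB324 capsules at study visits"). Section 11.2 does the same for erlotinib.

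**The concern.** The classes and the formula belong to different measures. Classes that run past 100% suit a ratio of drug taken to drug prescribed. The SAP formula only subtracts missed doses, so it has no term that could register extra intake. A reader of Table 14.1.8 who sees no patient above 120% could take that as a finding that nobody took too much, when no other result was possible.

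The denominator raises a second problem. Duration of administration in a cycle would normally end at the last dose, but the text then sets it to 21 days. The two differ only in a cycle cut short, and so only in patients who stop mid-cycle. The SAP does not say whether the days after permanent discontinuation are recorded as missed. One patient can therefore fall on either side of the 80% boundary, depending on an unwritten convention.

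**Working it through.** The plan gives no compliance figure to reproduce, so the formula was evaluated directly. Write E for expected and M for missed doses, so that C = 100 × (E − M)/E.

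**1. Upper limit**

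- M is a last date minus a first date, so M ≥ 0 and C ≤ 100%.
- In one 21-day cycle the lowest value comes from first missed Day 1 and last missed Day 21: M = 20 and C = 1/21 = 4.8%. The highest comes from M = 0: C = 21/21 = 100%.
- C > 120% would need M < −0.2 × 21 = −4.2, which valid dates cannot give.
- With no missed dose, C is exactly 100% for any number of cycles, so adding cycles does not lift the limit.

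**2. Extra intake**

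- 26 doses in 21 days: the SAP formula gives 100%; taken/expected gives 26/21 = 123.8%.
- Twice the prescribed capsules every day: the SAP formula gives 100%; taken/expected gives 42/21 = 200%.

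**3. Final cycle cut short**

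Last dose on Cycle 1 Day 8, with 3 doses missed before it. Doses taken = 8 − 3 = 5. Days after stopping = 21 − 8 = 13.

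| Handling | Calculation | Compliance |
|---|---|---|
| Days from first to last dose | 5/8 | 62.5% |
| Fixed 21, later days not logged, 3 missed counted as 3 | (21 − 3)/21 = 18/21 | 85.7% |
| Fixed 21, later days not logged, SAP missed count | (21 − 2)/21 = 19/21 | 90.5% |
| Fixed 21, later days logged as missed, true count | (21 − 3 − 13)/21 = 5/21 | 23.8% |

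The third row assumes the 3 missed days are consecutive. Last date minus first date, without adding 1, then counts them as 2.

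**4. Same patient with no missed dose before stopping**

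- First to last dose: 8/8 = 100%.
- Fixed 21, later days not logged: 21/21 = 100%.
- Fixed 21, later days logged, true count: 8/21 = 38.1%.

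Overstatement therefore needs both unlogged days after stopping and earlier missed doses.

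**5. Dilution over several cycles**

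Three full cycles, then a last dose on Day 10 of the fourth, with 3 doses missed in all:

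- Fixed 21, later days not logged: (84 − 3)/84 = 81/84 = 96.4%.
- First to last dose: (73 − 3)/73 = 70/73 = 95.9%.

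Under this handling, the denominator problem matters mainly for patients who stop in the first cycle or two.

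**The case against.** The strongest reply is that little depends on this table. Compliance is not among the safety endpoints in Protocol 7.5 or SAP 3.1. No hypothesis test or analysis population uses the percentage. Whether an Arm A patient is informative for dose escalation rests on loading doses received and daily doses missed (Protocol 8.3.2), not on this formula. The direct result of the 100% limit is one empty row and one mislabelled row. This stands, and it sets the weight of the point.

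A reader might infer that the plan hides overdosing. The documents do not support that beyond Table 14.1.8. SAP 5.6 also reports cumulative mg, Protocol 13.4.8 requires overdoses and incorrect administration to be noted on the eCRF, and SAP 6.2 lists drug accountability, exposure and administration.

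A reader might also infer that the fixed denominator always favours patients who stop early. The direction depends on a recording rule that the SAP omits: the error can be upward, downward or absent. It can also be said that the phrase about duration of administration already ends the count at the last dose. That reading is reasonable, but the 21 days stated straight after it contradict it, so a programmer has to guess.

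Finally, a reader might want patients above 115% counted in this table to mirror Protocol 13.4.8. A whole-treatment ratio would not do that. At a constant daily dose, one doubled day in 21 gives 22/21 = 104.8% and three give 24/21 = 114.3%, so real overdoses would stay below the line.

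**Conclusion.** The rule is wrong as written; its importance is minor. That compliance cannot exceed 100% follows from the SAP's own definitions and needs no assumption beyond valid dates. The above-120% class is therefore always empty, and the middle class is 80 to 100% under a wider label.

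The misstatement of a shortened final cycle is conditional. For the Day 8 patient with 3 missed doses, the true 62.5% becomes 85.7% to 90.5% if the days after stopping are not logged as missed, and 23.8% if they are logged and counted correctly. The first pair moves the patient from the lowest class to the middle one. The size assumes a single cycle and shrinks as full cycles accumulate.

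The effect is confined to a descriptive table. It does not reach the Arm B test, the populations or the dose-escalation decisions, and it does not show that the tolerability conclusion would be biased.

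**What to change.** Redefine compliance in SAP 5.6, separately for each drug, as 100 × amount taken / amount prescribed from first to last dose.

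- Take the numerator from the dosing diary and the capsule or tablet counts, and state which source is used when they disagree.
- Build the denominator from the amounts actually prescribed, including loading doses, prescribed reductions and prescribed interruptions.
- End the last cycle at the last dose, as the section's own duration definition does.
- Keep the three classes; all of them can then be reached.
- Do not add a 115% count. Overdoses under Protocol 13.4.8 are captured on the Study Drug Administration eCRF and should be reported from there.

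This also removes the missed-date subtraction from the formula. The cost is a change of SAP wording and reprogramming of Table 14.1.8; the protocol already provides for collecting the diary and accountability data.
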